### 9.7.6 Meta-analyses

Assuming country-specific analyses have been completed, results for the primary outcome analysis of NDD can also be combined across all three countries using a meta-analysis approach in order to achieve a more precise estimate of the observed effect size and identify any potential country-specific patterns in the data. A random effects meta-analysis will be applied assuming such heterogeneity in treatment effects exists. Cumulative incidence proportions and cumulative incidence rates of the two different exposure groups will be combined across the three databases. The HR of NDD including ASD in offspring paternally exposed to compared with offspring paternally exposed to lamotrigine or levetiracetam (composite monotherapy) will be calculated across the three databases

Results for the secondary outcome analysis of CM may also be similarly combined, although restricted to Norway and Denmark data only. The cumulative incidence proportion of the two

different exposure groups will be combined across the two databases, as well as the OR of CM in the two different exposure groups. The different start date for follow-up due to different data availability in the two countries can lead to heterogeneity in the type and nature of CM recorded, which in turn can have an impact on the precision of the estimate (see section 9.9 about limitations). For this reason a random effect meta-analysis will be conducted (53).

Between-database heterogeneity will be quantified with the  $I^2$  measure; results will be pooled using inverse variance weighting, where estimates with a lower variance are assigned a higher weight in the pooled estimate.

In order to meta-analyse cumulative incidence proportions (for both NDD including ASD and CM composite outcomes), risk ratio estimates will be obtained in each country as the ratio of the risk in the valproate paternally exposed group to the risk in the lamotrigine/levetiracetam paternally exposed group; inverse variance weighting will then be applied to the risk ratios. For cumulative incidence rate (for NDD including ASD composite outcome), the inverse variance weighting method will be applied to rate ratios (obtained as the ratio of the incidence rate in the valproate paternally exposed group to the rate in the lamotrigine/levetiracetam group). Hazard ratios from Cox PH regression analysis will be pooled across the three databases after having applied a logarithmic transformation; OR from logistic regression analysis will also be pooled across the Norway and Denmark databases; inverse variance weighting will be applied to these models' estimates.

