**Table 4: Potential confounding variables by outcome**

Outcome	Father
NDD, including ASD	
 
• Age
 
• Bipolar Affective Disorder and mania (ever)
 
• Calendar year of conception of offspring
 

CM	
 
• Age
 
• Calendar year of conception of offspring
 

NDD: Neurodevelopmental disorders; ASD: Autism Spectrum Disorder; CM: Congenital Malformations

**Paternal age.** Multiple epidemiological studies suggest a relationship between advanced paternal age at conception, and adverse neurodevelopmental outcomes (19,20) and congenital malformations (21–23) in offspring. This has been particularly noted with regard to increased risk for autism. ‘Paternal Age’ will be considered a confounding variable a priori, for both outcomes.

**Paternal Bipolar Affective Disorder and Mania.** Valproate is indicated in the treatment of epilepsy, mania and migraine (24). Moreover, children of parents diagnosed with mood disorders including mania have been shown to present with increased risk of neurodevelopmental outcomes. For these reasons, in this study, paternal bipolar affective disorder and mania will be considered as potentially confounding the effect of paternal valproate use on the development of neurodevelopmental disorders in offspring.

**Maternal epilepsy.** There is an increased risk of NDD, including ASD, and CM, in the offspring of female patients with epilepsy (25,26). However the high risk of NDD, including ASD in the offspring of female patients with epilepsy may be due to foetal exposure to AED medication in utero (2), including valproic acid. Offspring from women with epilepsy will only be included in the descriptive analyses of the sample from source population following data extraction, and excluded from the comparative, sensitivity and exploratory objective analyses.

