#### 9.7.2.2 *Incidence examination*

The cumulative incidence proportion, rate and time to onset of NDD, including ASD will be calculated as well as cumulative incidence proportion for composite CM endpoint and specific CM target body system organ groups based on ICD-10 codes. These statistics will be presented for each overall cohort and separately for offspring *paternally exposed to valproate or lamotrigine/ levetiracetam (composite and separately) in monotherapy 3 months prior to LMP2*.

The cumulative incidence (risk) of the primary outcomes reported each year will be explored by estimating the cumulative incidence of incident reports (plus 95% CI). For purposes of this analysis the denominator is defined according to the population initially at risk at the beginning of the study, since the estimates are cumulative; that is live births for NDD, including ASD and live plus non-live births for CM. The numerator will comprise of counts of incident events as recorded during each year and summed to reflect the cumulative count for all years up to that point. The cumulative incidence proportion will be calculated according to the formula:

$$\left( \frac{\text{Total number of offspring paternally exposed with newly diagnosed outcome during each cumulative year of interest}}{\text{Population initially at risk}} \right) \times 100$$

For each exposure group, the numerator for each year will contain the number of offspring for whom the incident outcome has been recorded in that year and will exclude offspring who have had an outcome previously, within the study period. The denominator will include offspring within the numerator and also offspring who did not have an outcome recorded in the current year or preceding years (i.e. only the ‘at risk’ population will be considered).

The cumulative incidence rate of the primary outcome will be modelled using survival methods and expressed as number of cases per 1000 patients-years at risk (+95%CI). Data may also be stratified according to other relevant strong risk factors for events of interest (age, gender) and stratum-specific incidence rates examined.

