For the time to event analysis of the primary outcome, a semi-parametric Proportional Hazards (PH) regression model will be derived to describe the time to event, which will be presented graphically. At least 10 cases will be required per event for crude estimates. A smoothed estimate of empirical hazard function will also be plotted using an epanechnikov kernel (bandwidth to be determined empirically from data). These will be used to describe how the baseline risk of an event changes over time.

In addition, cumulative incidence proportions for the entire period, 0-12 years for Denmark and Sweden and 0-10 years for Norway, will also be presented; this will be calculated as the

total number of offspring experiencing the outcome (NDD and CM, separately) during the entire follow-up (i.e. the sum of the number of events for the years 0 to 12 for Denmark and Sweden, and 0 to 10 for Norway) divided by the initial number of offspring included at the start of follow-up (i.e., population used in the analysis). Furthermore considering index date in the CM cohort will start before or on date of birth and that patients will be followed up until 12 years of age at maximum (10 years of age for Norway), there will be patients with a follow-up longer than 12 years (10 years for Norway), and therefore cumulative incidence proportion for the entire follow-up will include a longer period than 12 years for Denmark and Sweden (but shorter than 13 years). For Norway, the cumulative incidence proportion for the entire follow-up will include a longer period than 10 years, but shorter than 11 years.

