Once the propensity scores are estimated (separately for the primary and secondary outcome cohorts) they will then be used as weights in the inverse probability of treatment weights approach to balance differences in covariate distribution between offspring paternally exposed to valproate and offspring paternally exposed to lamotrigine/levetiracetam in the adjusted analyses. PS weighting will be used instead of matching for increased generalisability and to avoid the exclusion of patients from the adjusted analyses due to lack of matches (43–46); this is deemed as particularly important in situations where the outcome of interest is relatively rare or infrequent.

For each PS model, the distributions of estimated propensity scores will be visually compared across the three models, separately for the primary and secondary outcome. Selection of the best models for the primary and secondary outcome cohorts will be based on the balance achieved in the weighted exposure groups after using inverse probability of treatment weights. Only the best PS models for the primary and secondary outcome cohorts will then be used to apply inverse probability of treatment weights in the multivariate analysis.

The best PS modelling approach might not be the same for the two cohorts, and similarly the covariates included in the PS model will differ as the two outcomes have different risk factors and confounders.

A sensitivity analysis to compare the results from the PS-weighted approach with the traditional approach of covariate adjustment will be performed, as reported in section 9.7.5, for both primary and secondary composite outcomes, using the composite lamotrigine/levetiracetam monotherapy comparator.

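### As written, the risk ratios and rate ratios pooled across countries have no confounding adjustment, so they can diverge from the weighted HR and OR in either direction

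*Protocol*

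**What the plan says.** Section 9.7.2.2 defines the cumulative incidence proportion for each paternal drug group. The yearly numerator is the "Total number of offspring paternally exposed with newly diagnosed outcome during each cumulative year of interest", over those at risk at the outset. For the whole period the numerator is the "total number of offspring experiencing the outcome (NDD and CM, separately) during the entire follow-up", and that count is "divided by the initial number of offspring included at the start of follow-up". The figures are shown overall and for offspring "paternally exposed to valproate or lamotrigine/ levetiracetam (composite and separately) in monotherapy 3 months prior to LMP2". The NDD incidence rate is to come from survival methods, per 1,000 patient-years, with optional stratification by factors such as age and gender.

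Section 9.7.6 turns these into between-drug contrasts. For NDD and CM, "risk ratio estimates will be obtained in each country as the ratio of the risk in the valproate paternally exposed group to the risk" among comparator offspring. For NDD it also pools "rate ratios (obtained as the ratio of the incidence rate in the valproate paternally exposed group to the rate" among comparator offspring. Inverse variance weighting is then applied. The section gives greater precision for the effect size as a reason for pooling.

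Table 4 lists paternal age and calendar year of conception as confounders for both outcomes. For NDD, "paternal bipolar affective disorder and mania will be considered as potentially confounding the effect of paternal valproate use". Section 9.7.3.2.3 plans an "inverse probability of treatment weights approach to balance differences in covariate distribution" between valproate and the composite comparator, and assigns the resulting weights to the multivariate analysis. Sections 9.7.3.2.1 and 9.7.3.2.2 identify that analysis as the Cox HR for NDD and the logistic OR for CM, each in crude and weighted form.

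**The concern.** The protocol gives its own reasons to expect imbalance. Section 9.7.5, item 5, says that differing indications and licensing dates make the treated populations systematically different. Levetiracetam is dated there from 2000, while Section 9.2.1 starts the Danish NDD period in January 1997, so some imbalance in calendar year is to be expected.

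Two of the three pooled NDD contrasts, and one of the two pooled CM contrasts, are nevertheless specified without adjustment. They would stand beside the HR and OR in a regulator-requested safety study, and nothing in Section 9.7.6 or in the limitations (Section 9.9) marks them as unadjusted. No adjusted absolute risk is planned. A disagreement between the pooled risk ratio and the weighted HR could be taken for a finding about the drug when it only reflects who was prescribed it.

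**Working it through.** The protocol states no value for these risks or ratios, so there is no figure to reproduce. The check has two parts.

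**1. Which pooled measures carry an adjustment?**

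| Pooled measure | Outcome | Source | Confounding adjustment stated |
|---|---|---|---|
| Risk ratio | NDD, CM | group risks, 9.7.2.2 | none |
| Rate ratio | NDD | group incidence rates, 9.7.2.2 | none |
| HR | NDD | Cox model, 9.7.3.2.1 | weighted version planned |
| OR | CM | logistic model, 9.7.3.2.2 | weighted version planned |

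Inverse variance weights combine country estimates by precision. They do not balance the drug groups within a country. Optional stratification of rates by age or gender does not involve the paternal confounders in Table 4. That the first two rows are unweighted is inferred from the formulas and from where the treatment weights are assigned; Section 9.7.6 does not use the word.

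**2. How far could an unadjusted ratio move with no drug effect?**

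Take one binary confounder with prevalence pV in the valproate group and pC in the comparator group, which multiplies outcome risk by R. With no drug effect,

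crude RR = [1 + pV(R − 1)] / [1 + pC(R − 1)].

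The prevalences and R are assumptions; none is in the protocol.

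| R | 10% vs 20% | 10% vs 30% | 20% vs 10% | 30% vs 10% |
|---|---|---|---|---|
| 1.5 | 0.955 | 0.913 | 1.048 | 1.095 |
| 2 | 0.917 | 0.846 | 1.091 | 1.182 |
| 3 | 0.857 | 0.750 | 1.167 | 1.333 |

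(Columns are pV vs pC.) The extremes are (1 + 0.1×2)/(1 + 0.3×2) = 1.2/1.6 = 0.75 and the reverse, 1.6/1.2 = 1.33.

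To see what weighting does, take R = 2, 30% vs 10%, groups of equal size, and 4% risk in those without the confounder (the figure that Section 9.5 assumes for NDD in the reference group).

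- Crude risks: 4% × (1 + 0.3) = 5.2% and 4% × (1 + 0.1) = 4.4%; RR 1.18, difference 0.8 percentage points.
- Weighted to the combined prevalence of 20%: 4% × (1 + 0.2) = 4.8% in both groups; RR 1.00, difference 0.

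**The case against.** The strongest reply is that these are descriptive quantities. The incidence figures sit under the descriptive analyses; the inference rests on the weighted HR and OR, with a covariate-adjusted comparison in sensitivity analysis 6; and reporting crude results beside adjusted ones is normal. Section 9.7.6 does not call the ratios crude and is equally silent on whether the crude or weighted HR and OR are pooled, so the detail might belong in the SAP.

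Part of this stands. The main inference is protected, and keeping crude incidence is reasonable. But Section 9.7.6 converts the description into pooled valproate-versus-comparator ratios in a section that aims at a more precise effect size, and the protocol itself fixes how they are formed.

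Some stronger readings do not hold:

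- A reader might infer that the protocol requires this confounding to be removed from every estimate. It does not: it says the weights will balance covariates in the adjusted analyses, and it plans crude models too.
- A reader might infer that all these measures come from raw counts. That is true of the proportions; the rate is to be obtained by survival methods, though still with no stated adjustment for the Table 4 confounders.
- A reader might infer that existing weights cover everything in Section 9.7.2.2. They are built for valproate against the composite comparator. They do not serve lamotrigine and levetiracetam separately, nor offspring whom Section 9.7.3 excludes from the comparative analyses.

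**Conclusion.** The point holds in limited form. The cumulative incidence proportions by drug, the pooled risk ratios (NDD and CM) and the pooled NDD rate ratio have no confounding adjustment as the protocol is written. They can differ from the weighted HR or OR for reasons unrelated to the drug.

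Neither size nor direction can be read from the protocol. The range of about 0.75 to 1.33 rests on one assumed binary confounder, fully measured, with the prevalences and strengths shown. A reader might infer that the crude ratios must overstate harm from valproate because bipolar disorder is among its indications. The protocol does not support that: Section 9.7.5, item 5, notes that lamotrigine might also be prescribed for bipolar disorder, so the imbalance could be small or reversed.

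The weighted HR and OR, which carry the primary and secondary conclusions, are unaffected. Unequal length of follow-up between drug groups is a separate question and does not enter the range above.

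**What to change.** In Section 9.7.6, for valproate versus the composite comparator in the comparative-analysis cohort:

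- apply the existing inverse-probability weights to the cumulative incidence (at fixed ages for NDD) and to the NDD incidence rates;
- report the weighted risk difference, risk ratio and rate ratio with confidence intervals clustered on father;
- pool those.

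Keep the Section 9.7.2.2 figures, including lamotrigine and levetiracetam separately, as description. Label them, and any crude pooled ratio that is retained, as unadjusted.

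No new propensity model is needed for the composite contrast. The cost is some added programming, because weighted risks at fixed ages are a further estimator and not a reweighting of an existing table, and somewhat wider intervals from the weighting.

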#### **9.7.7 Handling of Missing Data**

Missing data are those where a variable is directly reported as missing or unavailable, where a variable observation is blank, where the extracted data may not be interpretable, or where the value must be imputed to be missing because of data inconsistency or out-of-range results.

Methods to handle issues of missing or conflicting data, will be summarised within the detailed study specific SAP which will be constructed to assist data analysis. In summary, the degree of data completeness and patterns of missingness will be summarized for all covariates proposed for inclusion in the regression analysis of the primary outcome of interest, and the regression analysis of the secondary outcome of interest using a pattern of missingness matrix. The number and proportion of missing data for each variable and the top five most frequent patterns of missingness will be presented. This descriptive analysis will be performed in order to explore which covariates have non-trivial proportions of missing data (>5%) and to examine the plausibility of the missing at random (MAR) assumption to justify any subsequent regression methods. A sensitivity analysis may be conducted to explore the impact of non-trivial proportions of missing data among key covariates and the subsequent bias that may occur in analyses restricted to participants with complete data ("complete case analysis") as in the primary and secondary outcome analysis. Appropriate imputation methods will be dependent on the amount of missing data and data type but may include use of the Multiple Imputation by Chained Equations (MICE).

### **9.8 Quality Control**

The study will use existing databases, which are being used widely for research. The study will be executed in line with all applicable regulations and guidelines – such as best-practice guidelines applicable to non-interventional PASS, including but not limited to the ENCePP Guide on Methodological Standards in Pharmacoepidemiology, the ENCePP Checklist for Study Protocols (Annex 2. ENCePP checklist for study protocols), and the Guidelines for Good Pharmacoepidemiology Practices of the International Society of Pharmacoepidemiology (ISPE

GPP) as well as the specific IQVIA Standard Operating Procedures (SOPs) on retrospective analysis.

For the IQVIA EU data sources, quality control is conducted at several levels depending on the database. At the database level, the quality unit of the production department of IQVIA verifies continuously the quality of its sources in terms of representativeness and consistency of collected data. All study programs, log files, and output files will be stored on the secure server. If the study is being conducted by a third party, the datasets and analytic programs will be stored according to the vendor's procedures.

## 9.9 Limitations of the Research Methods

### 9.9.1 Database limitations

The individual study databases have limitations typical of other registries databases:

- Data are collected only for administrative purposes, so some medical information not directly related to reimbursement may be incomplete or not available at all.
- As the data will be extracted from different country registries, some differences are expected in terms of variables collected, coverage and missing data patterns.
- Due to the imperative need to have family linkage of data, this study proposes to use databases from Norway, Sweden and Denmark, which allow this possibility. These countries are close from each other and all from the North of Europe. However, an important consideration in choice of study population is the generalizability (external validity) of the data source within a country, which can be defined as the degree to which the population covered by the database is representative of the total population.
- National databases such as those from the Nordic countries are known to be representative of the population of the country, typically contain lifetime data of patients and have demonstrably been used for research to reveal the real-world patterns. Furthermore more, choice of country and database selection is based on the ability for longitudinal record linkage between father, mother and offspring; this being a key requirement for this study.
- With regard to understanding the impact of genetic variability, this study will inform on whether an association exists between paternal use of AED in the pre-conception period and adverse effects in the offspring. Information on genetic profiling and ethnicity is not being collected therefore an evaluation of the hypothesised genetic mechanism for the proposed adverse effects, although relevant to the ongoing investigation, is not possible in this study.
- Information on breastfeeding is not available for Sweden and Norway, only limited data after 2012 for Denmark.
- Linkage to the father is not possible for induced abortion records in any country at study. It means that all diagnosis of CM followed by an induced abortion are not

---

detectable and not included in this study. It can lead to a selection of cases and to a survivor bias.

- Misclassification of paternal linkage is possible where the registered father is not the biological father of the offspring. All countries of interest include within their registries the possibility of identification of adoption or IVF. Offspring who were adopted or resulting from IVF are not included in this study. Paternal discrepancy can occur also when the offspring is identified as being biologically fathered by someone other than the man who believes he is the father. This was investigated by Bellis et al (54) who concluded that median paternal discrepancy is 3.7% (IQR=2.0%–9.6%).
- Information about spontaneous abortions and stillbirths (linked to mother and father) are not available for Denmark until 22nd week of pregnancy and for Norway until 12th week. It means that all diagnosis of CM for spontaneous abortions/stillbirths occurred before these weeks of gestation are not detectable and not included in this study. It can lead to a selection of cases and to a survivor bias. For purposes of the secondary analysis for CM, this will be conducted in Denmark and Norway only, where paternal linkage to non-live births is feasible. Sweden, where the linkage with fathers is not possible for non-live births, is not included in this analysis. However an exploratory analysis is proposed to explore risk of CM in live births, for completeness. The implications of having different definitions of the index date for the three countries should also be acknowledged. In brief, the relationship between the impact of a maternal exposure to a teratogen on normal embryonic and fetal differentiation and morphogenesis and week of gestation is well known. The distribution of type of CM and severity is likely to be different. Where data will be collected from 12th week of gestation, the distribution is likely to be biased towards major morphological abnormalities of which a high proportion will have a fatal outcome. Conversely where data are collected from 22nd week of gestation (Denmark) and from birth date of offspring (Sweden), the distribution is likely to favour functional defects and minor morphological abnormalities of which a high proportion will survive to term. In this regard the heterogeneity of outcome could be profound and have an impact on the precision of the estimate.
- Information on medicines without prescription purchased from a retailer is not available in the registers. It is a major limitation for medicines like folic acid that has a significant impact on frequency of Neural Tube Defects (NTD) and congenital heart defects (CHD). The findings of the Hungarian intervention (randomized double-blind and cohort controlled) trials indicated that periconceptional folic acid (FA)-containing multivitamin supplementation prevented the major proportion (about 90%) of NTD as well as a certain proportion (about 40%) of CHD defects (55). It is also reported in the literature that lack of folic acid supplementation in women with epilepsy treated with AED is associated with an 6-fold increased risk of autistic traits in their offspring at 18 months, or an eight fold increase in their offspring at 36 months

---

 In Denmark, induced abortion is allowed by law until 12 week of pregnancy, but a woman may also be granted an authorisation to abort after 12 weeks if certain circumstances are proved to be present (such as poor socioeconomic condition of the woman; risk of birth defects to foetus; the pregnancy being the result of rape; mental health risk to mother). In Norway, current legislation provides abortion on request in the first 12 weeks of gestation, by application up to the 18th week, and thereafter only under special circumstances until the foetus is viable.

depending on the instrument used, although this does not imply an increased risk of autism (56). The impact of failing to account for folic acid supplementation as an important confounder could lead to a bias in either direction in the estimate of risk of the pooled composite outcome of CM, or the pooled composite outcome of NDD, including ASD, in both exposure groups, however this is anticipated to be non-differential.

- Lifestyle factors (such as smoking or alcohol consumption) may not be available or may be incomplete. The negative effects of Prenatal Alcohol Exposure (PAE) on the developing brain and the resulting neurological and/or cognitive, behavioural, emotional, and adaptive functioning deficits in offspring maternally exposed *in utero* are well recognised (57). Alcohol-related NDD (ARND) refers to a complex range of disabilities in neurodevelopment and behaviour. Unlike Foetal Alcohol Syndrome (FAS), confirmed PAE cannot be identified phenotypically and therefore misclassification with other NDD or affective disorder is possible. Current prevalence estimates for FAS range from 0.5 to 7 cases per 1,000 live births in the United States, and the prevalence of FAS and ARND combined is thought to be three times that of FAS alone. In this study, there is no specific information on alcohol consumption and therefore the association between alcohol and ARND cannot be studied. Nevertheless, the potential impact on this study an overestimate of up to seven cases of the primary outcome of NDD per 1000 pregnancies when the alternative cause was potentially alcohol. However, this is anticipated to be non-differential, affecting both exposure groups equally.
- It is also well established that prenatal nicotine exposure, even through maternal smokeless tobacco use, is associated with numerous postnatal adverse health outcomes in newborns – not only low birth weight, preterm delivery, and sudden infant death syndrome but also severe neuropsychiatric disorders (58) (Tourette syndrome and chronic tic disorder (TS/CT), as well as TS/CT with comorbid psychiatric conditions including attention-deficit/hyperactivity disorder [ADHD]). With an estimated prevalence of up to ten cases per 1000 pregnancies the impact of misclassification can lead to an over estimation of effect of AED monotherapy on risk when the alternative cause was potentially prenatal nicotine. However, this is anticipated to be non-differential, affecting both exposure groups equally.
- In terms of the parental intelligence quotient (IQ) levels, such data are not available specifically in the registries and surrogate measures are often utilised. The potential impact of such missing data in this study is unclear, since there is conflicting evidence in the literature about the association between maternal AED exposure, maternal IQ and NDD in offspring. In a large prospective, observational, multicentre study, where data were available, the relationship between maternal IQ, maternal AED exposure and NDD (based on offspring IQ) in the offspring did not identify parental IQ as a risk factor (59). Conversely the results of a meta-analysis suggested higher parental IQ (based on a surrogate measure - parental education) is associated with increased risk of ASD (60) as a subtype of NDD (maternal education college graduate+[RR=1.58, 95% CI: 1.33, 1.88; P<.001], paternal education college graduate+[RR=1.54, 95% CI: 1.28, 1.87; P<.001]). Therefore, although potentially an important risk factor, the resulting bias from missing information may be in either direction and is also likely to be non-differential.

- Information on socioeconomic status (SES) is also not specifically available in the Nordic registries and surrogate measures are again often utilised. Similar to missing data for IQ, the potential impact on this study is unclear because conflicting evidence also exists in the literature. Epidemiological studies in the US consistently find ASD to be overrepresented in high SES families. However, a case-control study based within a Swedish county using council data reports that an inverse relationship exists such that risk is highest in subjects from lower SES (61). Their hypothesis for other studies not observing this relationship is based on under ascertainment of cases from lower SES groups in those studies. This is echoed in another recent publication in the US (62). It is also acknowledged that severe early deprivation has a causal role in NDD such as ADHD and is likely to apply to conditions such as ASD (63). The HOME scale for measuring adversity, does appear to correlate with risk of ADHD specifically, however more research is required to ascertain whether this is a causal association and the direction of causation (64). In summary, given these uncertainties, for this study, missing data on parental IQ and HOME are not considered a major limitation.
- Environmental and viral toxic substances factors are not available.
- For Scandinavian registry data, relatively long lag times has to be considered and they vary by country, for example the Swedish National Patient Register annual uptake is completed in September of the following year.
- For Denmark, when the outcome for a specific analysis will have less than five cases/observations, the specific result and other potentially related results, that could lead to the identification of those patients, will not be delivered from the data provider. It is a potential limitation for analyses that require many subclassifications, restrictions and stratifications, such as the exploratory analysis to investigate the risk of CM by target body system organ class. Furthermore, minimum and maximum values cannot be reported.

